5.6 Cardiovascular Guidelines

In response to findings of a modest increase in QT interval 24 hours post-dose, additional ECG monitoring is being incorporated into the protocol pending data from an ECG evaluation that is being performed within the context of Study 9090-14.

5.6.1 Patients at High to Moderate risk for torsades de pointes

For patients deemed at baseline by the treating investigator to be at moderate to high risk for torsades de pointes, the overall study PI should be consulted prior to registration to confirm the patient's eligibility for the study, given that patients with significant cardiovascular co-morbidities are excluded from the trial. It is not anticipated that patients with moderate or high risk of torsades will generally be enrolled onto the study. In the rare instance that such a patient meets all eligibility requirements, including cardiovascular eligibility requirements, ECGs are required at the following timepoints for patients receiving ganetespib:

- Baseline
- Cycle 1 Day 2 (approximately 24 hours post Cycle 1 Day 1 ganetespib dose)
- Pre-dose on Cycle 2 Day 1
- Approximately 24 hours post Cycle 2 Day 1 dose
- Pre-dose for each subsequent cycle
- Approximately 24 hours post Day 1 of each subsequent cycle

5.6.2 Patients at Low risk for torsades de pointes

For patients deemed at baseline by the treating investigator at low risk for torsades de pointes, ECG monitoring *in triplicate* is required at the following time points for patients receiving ganetespib:

- Baseline
- Cycle 1 Day 2 (approximately 24 hours post Cycle 1 Day 1 ganetespib dose)
- Pre-dose on Cycle 2 Day 1

If there is no evidence of QTc prolongation ($QTc > 470$ msec), subsequent EKGs are required:

- Pre-dose, day 1 of each cycle

CONFIDENTIAL

This document is confidential. Do not disclose or use except as authorized.

If there is evidence of QTc prolongation ($QTc > 470$ msec) on the pre-dose EKG, the patient is required to return for a repeat EKG ~24 hours post-ganetespib dose (applies to all cycles of treatment).

If a patient has a reported $QTc \geq 501$ ms (QTc prolongation Grade 3 severity), at any ECG (an average of triplicate recordings), the patient may continue ganetespib treatment at a reduced dose of 120 mg/m² after the QTc has decreased to at least < 470 ms.

If a patient has a reported $QTc \geq 501$ ms or > 60 ms change from baseline and torsades de pointes or polymorphic ventricular tachycardia or signs/symptoms of serious arrhythmia (QTc prolongation Grade 3 severity) or repeated Grade 3 or higher QTc prolongation, the patient must discontinue treatment with ganetespib.

If a patient has a dose reduction or discontinues treatment due to QTc prolongation, the patient should have additional ECG monitoring in triplicate until the QTc interval returns to baseline.

Patients with QTc prolongation of grade 3 severity or higher should be closely monitored during the first 72 hours post ganetespib infusion (i.e. electrolytes, concomitant medications) and at subsequent cycles of ganetespib treatment.

Because of the QT study findings of a modest increase in QT interval prolongation at 24 hours post dose, certain drugs should not be used by patients being treated with ganetespib. The use of any medication that has the potential for QTc prolongation **and** has been linked to the occurrence of torsades de pointes is strictly prohibited. See Appendix I for a list of drugs with a risk of torsades de pointes. Investigators should note that Zofran (ondansetron) has been linked to QTc prolongation and the occurrence of torsades de pointes. Therefore it should not be used in patients being treated with ganetespib. The use of all other serotonin 5 HT₃ antagonists is acceptable (e.g., palonsetron, granisetron, tropisetron).

Medications that have the potential of prolonging the QT interval but are not linked to the occurrence of torsades de pointes should be avoided or used with caution. The decision to use such a medication should be made by the Investigator, taking into consideration the patient's medical history and current QTc value. In addition, Investigators should optimize patients' electrolyte status and correct serum magnesium, potassium, and calcium as clinically indicated.

5.7 Duration of Therapy

Duration of therapy will depend on individual response, evidence of disease progression and tolerance. In the absence of treatment delays due to adverse events, treatment may continue until one of the following criteria applies:

- Disease progression,
- Intercurrent illness that prevents further administration of treatment,
- Unacceptable adverse event(s),

CONFIDENTIAL

This document is confidential. Do not disclose or use except as authorized.

- Participant decides to withdraw from the study, or
- General or specific changes in the participant's condition render the participant unacceptable for further treatment in the opinion of the treating investigator.
- At the discretion of the MD, investigator, or Sponsor

Patients who are randomized to Arm A may cross over to Arm C and receive combination therapy with fulvestrant + ganetespib at the time of centrally confirmed progression. Treatment may then continue on the combination until one of the above criteria applies.

It is anticipated that some patients in Arm B or Arm C may either choose or be taken off of ganetespib for reasons other than disease progression (i.e. for toxicity or patient preference). The following guidelines apply:

- Patients who are taken off of ganetespib for toxicity at any time should remain on study and continue fulvestrant. Restaging evaluations and clinic visits should continue on the protocol mandated schedule until either disease progression, intercurrent illness that prevents further administration of treatment, unacceptable adverse event(s), the participant decides to withdraw from the study, or general or specific changes in the participant's condition render the participant unacceptable for further treatment in the opinion of the treating investigator.
- Patients being treated with fulvestrant + ganetespib whose disease remains stable or in response for at least 6 cycles may elect to discontinue ganetespib. Once ganetespib is discontinued, it will not be restarted. Patients who discontinue ganetespib should remain on study and continue fulvestrant. Restaging evaluations and clinic visits should continue on the protocol mandated schedule until either disease progression, intercurrent illness that prevents further administration of treatment, unacceptable adverse event(s), the participant decides to withdraw from the study, or general or specific changes in the participant's condition render the participant unacceptable for further treatment in the opinion of the treating investigator.
- Patients who are taken off fulvestrant and/or ganetespib for any reason other than centrally-confirmed progression or death should be followed according to study calendar D until evidence of disease progression, start of new anti-cancer therapy, withdrawal of consent for follow-up, or death, whichever comes first.

5.8 Duration of Survival and Adverse Event Follow Up

Participants will be followed for survival for up to 4 years after the last dose of protocol therapy or until death, whichever occurs first. Participants removed from study for unacceptable adverse events will be followed until resolution or stabilization of the adverse event.

5.9 Criteria for Removal from Study

Participants will be removed from study treatment when any of the following occur:

CONFIDENTIAL

This document is confidential. Do not disclose or use except as authorized.

- Disease progression,
- Start of new anti-cancer therapy, or
- Participant decides to withdraw from the study treatment
- Subject death

Note: Patients in Arm A who progress on fulvestrant alone may first cross over to Arm C (fulvestrant + ganetespib).

Participants will be considered ‘Off Study’ when one of the following events occurs:

- Death
- Participant decides to withdraw from the study follow-up procedures
- 4 years after the date of the last study treatment dose

Note: Patients on either arm who discontinue assigned protocol treatment (fulvestrant and/or ganetespib) for any reason other than progression or death *should not be removed from study but instead should continue to be followed per protocol (See Study Calendar D) until evidence of disease progression, start of new anti-cancer therapy, withdrawal of consent for follow-up, or death, whichever occurs first.*

The reason for study removal and the date the participant was removed must be documented in the study-specific case report form (CRF). Alternative care options will be discussed with the participant.

In the event of unusual or life-threatening complications, participating investigators must immediately notify the Principal Investigator (or Protocol Chair), [name] at [contact], [name].

6. EXPECTED TOXICITIES AND DOSING DELAYS/DOSE MODIFICATIONS

Dose delays and modifications will be made using the following recommendations. Toxicity assessments will be done using the CTEP Active Version of the NCI Common Terminology Criteria for Adverse Events (CTCAE) v 4.0 which is identified and located on the CTEP website at: http://ctep.cancer.gov/protocolDevelopment/electronic_applications/ctc.htm.

If possible, symptoms should be managed symptomatically. In the case of toxicity, appropriate medical treatment should be used (including anti-emetics, anti-diarrheals, etc.).

All adverse events experienced by participants will be collected from the time of the first dose of study treatment, through the study and until the final study visit. Participants continuing to experience toxicity at the off study visit may be contacted for additional assessments until the toxicity has resolved or is deemed irreversible.

CONFIDENTIAL

This document is confidential. Do not disclose or use except as authorized.

6.1 Anticipated Toxicities

A list of the adverse events and potential risks associated with the agents administered in this study appear below and will determine whether dose delays and modifications will be made or whether the event requires expedited reporting **in addition** to routine reporting.

6.1.1 Adverse Event Lists(s) for ganetespib

Aggregate clinical data across all dose levels from the ongoing clinical studies show the following adverse events (AEs) of all grades as most common (>10%) by the Medical Dictionary for Regulatory Activities (MedDRA) preferred term:

- Diarrhea (72%)
- Abdominal pain (22%)
- Fatigue (51%)
- Insomnia (16%)
- Dyspnoea (17%)
- Anorexia (22%)
- Increase in aspartate aminotransferase (AST) (14%)
- Increase in alkaline phosphatase (AP) (13%)
- Nausea (37%)
- Vomiting (20%)
- Peripheral edema (15%)
- Anemia (24%)
- Constipation (15%)
- Increase in alanine aminotransferase (ALT) (11%)
- Headache (18%)
- Back pain (15%)
- Dizziness (13%)
- Hypokalemia (11%)
- Pyrexia (11%)
- Dehydration (10%)
- Skin rash (10%)

Diarrhea is experienced by virtually all subjects treated at therapeutic doses. Based on clinical experience to date, over-the-counter medications such as diphenoxylate and atropine sulfate (Lomotil[®]) and loperamide (Imodium[®]) mitigate the severity and duration of the diarrhea. It is recommended that medications, such as those listed above, should be utilized before ganetespib administration and before the onset of GI symptoms. (See Protocol section 5.5 for recommended dosing instructions)

Fatigue is observed in up to 50% of patients, mostly NCI CTCAE grade 1. Some subjects have experienced grade 2 or 3 fatigue, which was managed by study drug dose reduction

CONFIDENTIAL

This document is confidential. Do not disclose or use except as authorized.

per protocol. In some subjects, medications (e.g. Ritalin) were used successfully to manage fatigue.

To date, severe liver toxicity has not been observed. In some subjects, transient elevations of transaminases or bilirubin have been observed, typically CTCAE grade 1 or 2; however a few grade 3 elevations were observed.

6.1.2 Adverse Event List(s) for fulvestrant

The side effect profile includes injection site pain (9-12% of patients), nausea (10-13%), and bone pain (~10%). In the CONFIRM trial, the most commonly reported toxicities (any grade) on the 500 mg arm were GI disturbances (20%), joint disorders (19%), injection site reactions (14%), and hot flashes (8%).⁶ The most common grade 3 or higher toxicities were GI disturbances (2%) and joint disorders (2%). Other grade 3 or higher toxicities were uncommon and did not exceed 1% frequency in this study. Please refer to the package insert for a comprehensive list of adverse events.

6.2 Dose Modifications/Delays

Dose delays and modifications will be made using the following rules. Toxicity assessments will be done using the CTEP Active Version of the NCI Common Terminology Criteria for Adverse Events (CTCAE) v 4.0 which is identified and located on the CTEP website at:

http://ctep.cancer.gov/protocolDevelopment/electronic_applications/ctc.htm.

6.2.1 Ganetespib

Dose Level	Dose	Route	Schedule	Cycle Length
Starting dose	200 mg/m ²	IV	D1, 8, 15	28 days
First dose reduction	175 mg/m ²	IV	D1, 8, 15	28 days
Second dose reduction	150 mg/m ²	IV	D1, 8, 15	28 days

As detailed in Sections 5.1 and 14.2, at the time of initial study design, it was decided that in the case of more than 2 DLTs within the first 10 patients on Dose Level 1 (starting dose 200 mg/m²), the study would close temporarily to accrual while the events were adjudicated. Based upon results of this adjudication, the study would re-open at Dose Level -1 (starting dose 175 mg/m²). In this event, there would be only 1 allowed dose reduction (i.e. to 150 mg/m²) for patients entered at this starting dose level. Once decreased, doses would NOT be re-escalated. This DLT rule was not triggered for the first 10 patients randomized to Arm B; therefore enrollment to Arm B has continued at Arm B Dose Level 1 and treatment on Arm C has continued at Arm B Dose Level 1.

If possible, symptoms should be managed symptomatically. In the case of toxicity, appropriate medical treatment should be used (including anti-emetics, anti-diarrheals, etc.).

CONFIDENTIAL

This document is confidential. Do not disclose or use except as authorized.

All adverse events experienced by participants will be collected from the time of the first dose of study treatment, through the study and until the final study visit. Participants continuing to experience toxicity at the off study visit may be contacted for additional assessments until the toxicity has resolved or is deemed irreversible.

The following guidelines are provided for the modification of dose of ganetespib in the event of toxicities attributed by the investigator to this drug. Toxicities unrelated to ganetespib will not ordinarily result in modification of ganetespib dose.

Once a dose has been reduced, it should not be re-escalated.

Missed doses should be *skipped*, rather than held. Therefore, one cycle will nearly always be 4 weeks, allowing time for vacation, holidays, etc.

CONFIDENTIAL

This document is confidential. Do not disclose or use except as authorized.

Dose Modification Guidelines for Ganetespib

Toxicity	Grade	Guideline for management	Ganetespib dose modification*
Diarrhea	1	See Section 5.5	None
	2	See Section 5.5	None; If unacceptable to patient or medically concerning despite maximal supportive measures, then skip until recovery to \leq grade 1 (or baseline), up to 21 days*. Restart at same dose**.
	≥ 3		If grade 3 or greater despite maximal supportive measures, skip until recovery to \leq grade 1 (or baseline), up to 21 days*. And then Reduce 1 dose level.
Nausea/vomiting	1 or 2	Treatment as appropriate.	None
	3 (First or 2 nd occurrence)	Treatment as appropriate.	Skip until recovery to \leq grade 1 (or baseline), up to 21 days*. And then Restart at same dose.
	3 (3 rd or more occurrence)		If grade 3 or higher despite optimal prophylactic measures, then skip until recovery to \leq grade 1 (or baseline), up to 21 days*. And then Reduce 1 dose level.
Fatigue	1	No intervention	None
	2	Treatment as appropriate.	None; If unacceptable to patient or medically concerning then hold until recovery to \leq grade 1 (or baseline), up to 21 days*. Restart at same dose**.
	3	Treatment as appropriate.	Skip until recovery to \leq grade 1 (or baseline), up to 21 days*. And then Reduce 1 dose level.
Other non-Hematologic toxicity	1	No Intervention	None
	2	Treatment as appropriate	None; If unacceptable to patient or medically concerning then skip until recovery to \leq grade 1 (or baseline), up to 21 days*. Restart at same dose**.
	2 prolonged or clinically significant and grade ≥ 3	Treatment as appropriate	Skip until recovery to \leq grade 1 (or baseline), up to 21 days And then Reduce 1 dose level*

CONFIDENTIAL

This document is confidential. Do not disclose or use except as authorized.

Toxicity	Grade	Guideline for management	Ganetespiib dose modification*
Infusion reactions	3	Treatment per institutional guidelines for infusion reactions	Contact Principal Investigator to determine whether patient may be retreated
	4	Stop infusion	Permanently discontinue
Thrombocytopenia	1 or 2	No intervention	None
	3	No intervention	Skip until recovery to \leq grade 1 (or baseline), up to 21 days And then Reduce 1 dose level*
Hemoglobin	1 or 2	Treatment as appropriate	None
	3	Treatment as appropriate	Skip until recovery to \leq grade 1 (or baseline), up to 21 days And then Reduce 1 dose level*
Neutropenia	1 or 2	No intervention	None
	3 (ANC < 1,000/ μ L) lasting > 7 days		Skip until recovery to \leq grade 1 (or baseline), up to 21 days And then Reduce 1 dose level*
Cardiac toxicity	3 (first occurrence of QTc \geq 501 ms on average of triplicate recordings)		Reduce dose level to 120 mg/m ² after the QTc has decreased to at least < 470 ms.
	3 (repeat occurrence of QTc \geq 501 ms on average of triplicate recordings)		Permanently discontinue
	4 (QTc \geq 501 ms or > 60 ms change from baseline and torsades de pointes or polymorphic ventricular tachycardia or signs/symptoms of serious arrhythmia)		Permanently discontinue

* if no recovery after 21 days, patients should go off study

** if dose has been previously held for grade 2 toxicity and grade 2 symptoms recur, OR if the patient finds the symptoms unacceptable, hold dose until recovery to \leq grade 1 and then reduce dose one level

In the case of grade 4 hematologic or non-hematologic toxicity, ganetespiib should be skipped until recovery to grade 1 or less (or baseline), up to 21 days, and then the dose reduced to 150 mg/m². Subjects unable to tolerate ganetespiib at a dose level of 150 mg/m² or whose ganetespiib related toxicity has not returned to baseline or Grade \leq 1 within 21 days should stop ganetespiib. Patients may continue on fulvestrant alone at this time. Once permanently discontinued, ganetespiib should not be restarted.

In the case of a recurrent grade 3 event after prior dose reduction, ganetespiib should be held until the related toxicity has returned to baseline or Grade \leq 1. Subjects should be

CONFIDENTIAL

This document is confidential. Do not disclose or use except as authorized.

reduced by 1 additional dose level (i.e. 2 dose levels from baseline) upon restarting study drug. Only 2 dose reductions are allowed per protocol.

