- Patients who are taken off of ganetespib for toxicity at any time should remain on study and continue fulvestrant. Restaging evaluations and clinic visits should continue on the protocol mandated schedule until either disease progression, intercurrent illness that prevents further administration of treatment, unacceptable adverse event(s), the participant decides to withdraw from the study, or general or specific changes in the participant's condition render the participant unacceptable for further treatment in the opinion of the treating investigator.
- Patients being treated with fulvestrant + ganetespib whose disease remains stable or in response for at least 6 cycles may elect to discontinue ganetespib. Once ganetespib is discontinued, it will not be restarted. Patients who discontinue ganetespib should remain on study and continue fulvestrant. Restaging evaluations and clinic visits should continue on the protocol mandated schedule until either disease progression, intercurrent illness that prevents further administration of treatment, unacceptable adverse event(s), the participant decides to withdraw from the study, or general or specific changes in the participant's condition render the participant unacceptable for further treatment in the opinion of the treating investigator.

As part of the clinical trial, ganetespib will be provided free of charge to study participants by Synta Pharmaceuticals. Patients and/or their insurance companies will be billed for the cost of fulvestrant, which will come from commercial supply.

Arm A					
Agent	Pre-medications	Dose	Route	Schedule	Cycle Length

CONFIDENTIAL

This document is confidential. Do not disclose or use except as authorized.

Fulvestrant	None	500 mg	Intramuscular injection	C1: D1, D15 C2: D1 Then on Day 1 of each subsequent cycle	28 days (4 weeks)
-------------	------	--------	-------------------------	---	-------------------

CONFIDENTIAL

This document is confidential. Do not disclose or use except as authorized.

Arm B: Dose Level 1					
Agent	Pre-medications*	Dose	Route	Schedule	Cycle Length
Fulvestrant	None	500 mg	Intramuscular injection	C1: D1, D15 C2: D1 Then on Day 1 of each subsequent cycle	28 days (4 weeks)

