5.1.15 PFS Follow-up Procedures

Because the primary endpoint of the study is PFS, patients who are taken off treatment for any reason other than disease progression will REMAIN ON PROTOCOL and continue with the protocol mandated schedule of events (i.e. staging studies) until progressive disease, start of new anti-cancer therapy, or death, whichever comes first. For example, patients who are randomized to Arm B (fulvestrant + ganetespib) and who discontinue ganetespib without evidence of progression should continue on fulvestrant alone and continued to be followed for progression with staging studies/evaluations per protocol.

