9.4 STUDY CALENDAR D

Calendar of Events for Patients who Discontinue Study Treatment for Reasons Other than Progression or Death.

As detailed in Section 5.6 and Section 5.8, participants will be removed from study when any of the following occur

- Disease progression,
- Start of new anti-cancer therapy, or
- Participant decides to withdraw from the study follow up procedures
- Subject death

Prior to removal from study, patients in Arm A who progress on fulvestrant alone may first cross over to the combination arm. Patients in Arm A who discontinue fulvestrant for any reason other than centrally confirmed progression or death, and who do not cross over should continue to be followed according to the study calendar below, **until evidence of disease progression, start of new anti-cancer therapy, withdrawal of consent to follow-up, or death, whichever occurs first.**

For patients in Arm B or Arm C, once ganetespib is discontinued for any reason, patients **should not be removed from study but instead should remain on fulvestrant and continue to be followed per protocol according the study calendar below, until evidence of disease progression, start of new anti-cancer therapy, withdrawal of consent to follow-up, or death, whichever occurs first .** Patients who choose to discontinue fulvestrant without evidence of disease progression should also be followed per protocol, as specified below, until evidence of disease progression, start of new anti-cancer therapy, withdrawal of consent to follow-up, or death, whichever occurs first.

	Every 4 weeks	Every 8 weeks	Off-Study	Follow-Up
Concurrent medications	X		X	
Physical examination	X		X	
Vital signs ^a	X		X	
ECOG performance status	X		X	
CBC w/diff, plts		X	X	
Serum chemistry ^b		X	X	
CEA, CA27-29			X ^c	
Adverse event evaluation ^e	X		X	
Tumor measurements ¹		X ¹	X	
Bone scan ¹		X	X	
Fulvestrant, if applicable (see above)	X			
Research Specimen Collection (see section 9.5)			X	

CONFIDENTIAL

This document is confidential. Do not disclose or use except as authorized.

Survival Status (see section 5.1.16)				X q3 months
---	--	--	--	----------------

- a. Vital signs: heart rate, blood pressure, respiratory rate
- b. Serum chemistry: sodium, potassium, chloride, bicarbonate, blood urea nitrogen, creatinine, glucose (random), total bilirubin, alkaline phosphatase, ALT, AST, albumin, calcium, magnesium, phosphorus

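### The ganetespib dose-table footnote takes patients with unresolved toxicity off study, against the protocol's own PFS follow-up rules and in Arm B only

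*Combined protocol and SAP*

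**What the plan says.** In section 6.2.1 the dose-modification table lets ganetespib be skipped for up to 21 days while a toxicity resolves. An asterisk on the dose-modification column heading, and on most of the rows with that rule, leads to this footnote: "if no recovery after 21 days, patients should go off study".

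The paragraph under the table covers the same 21-day failure to recover. It stops ganetespib and adds: "Patients may continue on fulvestrant alone at this time".

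Other sections give the rule for patients who stop ganetespib without progression:

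- Section 5, repeated in 5.7: "Patients who are taken off of ganetespib for toxicity at any time should remain on study and continue fulvestrant".
- Section 5.1.15, which gives the primary endpoint as the reason: "patients who are taken off treatment for any reason other than disease progression will REMAIN ON PROTOCOL".
- Section 5.7, last bullet: such patients "should be followed according to study calendar D until evidence of disease progression".
- Section 5.9, note: they "should not be removed from study but instead should continue to be followed per protocol (See Study Calendar D) until evidence of disease progression".
- Section 9.4, Study Calendar D, for Arms B and C: they "should not be removed from study but instead should remain on fulvestrant and continue to be followed per protocol according the study calendar below".

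Section 5.9 also lists the only three events that make a participant off study: death, withdrawal from follow-up, and "4 years after the date of the last study treatment dose". Toxicity is not among them.

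Under section 14.2, PFS without an event is censored at the last tumor evaluation. The sample size allows for 11 of 71 patients (15%) being censored early and takes that probability to be the same in both arms.

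**The concern.** The footnote and the paragraph beneath it cannot both be followed as written. The footnote sits in the table that a treating physician opens when toxicity occurs, so it may be read without sections 5 or 9.

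The instruction also reaches only one arm before first progression. Arm A patients receive ganetespib only after centrally confirmed progression (section 9.3), and fulvestrant has no dose modifications (section 6.2.2). Literal use would end PFS follow-up early in Arm B alone. If the patients lost this way differ in prognosis from the rest, the comparison is biased. If they do not, some events and a little power are lost.

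Two other pieces of text leave the same gap. The restaging bullets in sections 5 and 5.7, written for patients taken off ganetespib for toxicity, include unacceptable adverse events among the reasons to stop restaging. Study Calendar B (section 9.2) provides for Arm B patients who, for whatever reason, are not followed on Calendar D and then have survival follow-up only.

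**Working it through.** **1. The instructions side by side, for a patient whose ganetespib toxicity has not resolved at 21 days**

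| Place | Study drug | Progression follow-up |
|---|---|---|
| 6.2.1, footnote | not stated | ends, if off study is read literally |
| 6.2.1, paragraph below | stop ganetespib; fulvestrant optional | not stated |
| 5 and 5.7, toxicity bullet | continue fulvestrant | continues, but may end at an unacceptable adverse event |
| 5.1.15 | continue fulvestrant (its Arm B example) | continues to progression, new therapy or death |
| 5.7, last bullet; 5.9, note | not stated | continues on Calendar D |
| 9.4, Calendar D | continue fulvestrant | continues on Calendar D |

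The footnote is the only entry that takes the patient off study.

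**2. The plan's own figures reproduce**

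Inputs from section 14.2: effective sample 20 v 40, exponential PFS with medians 4 and 8 months (hazard ratio 0.5), 20 months' accrual plus 20 months' follow-up, one-sided 0.05 log-rank test, 57 expected events.

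Expected events per arm are n × {1 − [exp(−λF) − exp(−λ(A+F))] / (λA)}, with λ = ln 2 / median and A = F = 20:

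- Arm A: 19.8
- Arm B: 36.6
- Total: 56.5, against the stated 57

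Power by Schoenfeld's formula is Φ(√(57 × 1/3 × 2/3) × ln 2 − 1.645) = Φ(2.467 − 1.645) = 0.794. Log-rank simulation gives 0.80. The plan states 80%.

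**3. Literal use of the footnote**

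The documents give no rate of non-recovery, so the affected share is assumed: 5% of 47 is 2.35 patients and 20% is 9.4.

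*Null simulation.* 24 v 47 patients, both medians 4 months, accrual and follow-up as above. The affected share, present in both arms, has the hazard ratio shown. In Arm B only, those patients are censored at a uniform 1 to 3 months. There are 300,000 trials per setting, each analysed with and without the footnote. Without it the one-sided type I error is about 6.0% (5.9 to 6.1%); its excess over the nominal 5% is not caused by the footnote. Changes in percentage points:

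| Hazard ratio of affected patients | 3% share | 5% | 10% | 20% |
|---|---|---|---|---|
| 0.5 | -0.8 | -1.2 | -2.1 | -3.5 |
| 0.67 | -0.4 | -0.7 | -1.3 | -2.3 |
| 1.0 | 0.0 | 0.0 | 0.0 | -0.1 |
| 1.5 | +0.3 | +0.4 | +0.9 | +1.7 |
| 2.0 | +0.4 | +0.6 | +1.2 | +2.5 |

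The null PFS hazard ratio (B to A) moves from 1.00 to 1.04 (affected hazard ratio 0.5) or 0.99 (2.0) at a 5% share, and to 1.14 or 0.95 at 20%.

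*Power simulation.* Medians 4 v 8 months, 11/71 = 15.5% lost at entry in both arms, 200,000 trials per setting. The base without the footnote and without a prognosis link is 79.9% power and 56.5 events. Where prognosis differs, the base is 74.7 to 79.5%, and changes are taken from that base.

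| | 3% share | 5% | 10% | 20% |
|---|---|---|---|---|
| Events, no prognosis link | 55.6 | 55.0 | 53.5 | 50.5 |
| Power change (points), no link | -0.3 | -0.5 | -1.1 | -2.6 |
| Power change, hazard ratio 0.5 | -2.0 | -3.5 | -7.3 | -15.4 |
| Apparent change, hazard ratio 2.0 | +0.9 | +1.5 | +2.9 | +5.5 |

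The last row is bias, not a gain. A separate, smaller simulation (20 v 40 patients, exit at 0.75 to 2.75 months, no link) gave 54.9, 53.3 and 50.3 events, and power of 0.79, 0.79 and 0.76, at shares of 5, 10 and 20%.

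**The case against.** The strongest reply is that one footnote stands against a protocol that is otherwise clear. Besides the places quoted above, the first bullet of Calendar B sends Arm B patients who stop ganetespib without progression to Calendar D. The PFS definitions in 10.1.8 and 14.2 do the same, and 14.6.3 requires PFS assessment of every randomized patient despite major treatment deviations. Off study may also simply mean off ganetespib: the asterisk is on the ganetespib column, and section 5.1.13 speaks of off-study for toxicity while still planning central review of PFS. All of this is correct. It makes literal use less likely and keeps the point minor, but the contradictory instruction is still in the table.

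A second reply is that the log-rank test needs non-informative censoring, not equal censoring, and that the equal-probability statement in 14.2 is only a planning assumption. That also stands. The hazard ratio 1.0 row shows essentially no change in type I error, so any bias depends on a link with prognosis that the documents neither establish nor give a direction for.

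A third is that the simulated inputs are assumptions and the extreme cells are remote. That is fair. The 15.4-point loss needs a 20% share, a hazard ratio of 0.5, the footnote applied to every affected patient and no later event captured. Two patients could also fall within the plan's allowance of 11. The null runs omit the early loss that the power runs include, so the two sets have slightly different bases.

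**Conclusion.** The footnote is wrong as written, at minor severity. It contradicts its own section and the PFS follow-up rules, and before first progression it can affect only Arm B.

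The effect is probably small. Section 2.1 describes diarrhea, the most frequent toxicity, as lasting 24 to 48 hours after infusion, which suggests that few patients would fail to recover within 21 days. At an assumed 5% share the change in type I error lies between -1.2 and +0.6 points, and the power loss without a prognosis link is 0.5 points. The bias favours the combination if affected patients do worse and runs against it if they do better.

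The simulated figures are at the upper end for each assumed share. They suppose that every affected patient is dropped and that no later progression or death is recorded, although the survival contacts in 5.1.16 could still supply deaths.

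**What to change.** 1. Replace the footnote with: *if no recovery after 21 days, permanently stop ganetespib; the patient remains on study, should continue fulvestrant, and is followed per Study Calendar D until progression, new anti-cancer therapy, withdrawal of follow-up consent or death.*
2. In the paragraph below the table, change *may* to *should* for continuing fulvestrant alone, to match sections 5, 5.7 and Calendar D. This only harmonises the wording, because Calendar D already follows patients who stop fulvestrant.
3. In the restaging bullets of sections 5 and 5.7, let adverse events end treatment but not progression follow-up, as the last bullet of 5.7 already requires.

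The cost is a wording amendment. Calendar D already requires the scans and visits.
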